10.4.3 ANALYSIS OF THE SECONDARY ENDPOINT(S)

This study does not have any powered secondary endpoints. All clinical and other process endpoints are exploratory.

10.4.4 SAFETY ANALYSES

This is a small clinical trial. We will summarize SAEs by study group (early transport versus usual care) and provide a listing of all SAEs for each of the patients in the intent to treat population.

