2.3 POTENTIAL RISKS AND BENEFITS

2.3.1 KNOWN POTENTIAL RISKS

Risks of mechanical or traditional CPR: bruising and soreness of the chest is common after mechanical or traditional CPR. Pneumothorax and hemo-pericardium are also possible risks. Rib fractures and solid organ injuries (liver and spleen) are additional potential risks.

Risk of EMS (early transport): motor vehicle crash during transport to the hospital.

Alternatives to early transport with mechanical CPR: Continued BLS and ACLS at the scene with manual or mechanical CPR until ROSC is achieved or resuscitation efforts are terminated (current practice).

Risks of ECPR (standard care procedure in hospital): vascular injury, limb ischemia, major hemorrhage, venous thromboembolism, stroke, renal failure, and infection.

Alternatives to ECPR for refractory cardiac arrest: An option is to transport patients to the interventional cardiology laboratory with ongoing CPR for coronary angiography and PCI if indicated. The rationale for this approach is that an acute coronary occlusion is the cause of the cardiac arrest and treating that occlusion could result in ROSC. At this time there is less evidence to support this approach compared to ED-initiated ECPR followed by coronary angiography and PCI following initiation of ECPR if indicated.

Risks of research: improper disclosure or release of personal or medical information.

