3 OBJECTIVES AND PURPOSE

Co-Primary: To determine what proportion of patients with refractory OHCA can be delivered to an ECPR-capable ED within 30 min of the 911 call or prehospital provider witnessed first cardiac arrest (qualifying OHCA event). This is to establish the feasibility of the early transport protocol.

Co-Primary: To determine what proportion of patients can have ECPR initiated within 30 minutes of ED arrival for patients with ongoing refractory OHCA. This is to establish the feasibility of the ED advanced resuscitation protocol in situations where prenotification of the team has occurred by qualified prehospital providers.

Safety: To estimate frequency of adverse events associated with study interventions. This early phase trial is not adequately sized to provide meaningful comparative estimates. The

population of OHCA survivors is at high risk for death and adverse experiences under routine clinical care.

Exploratory: Demonstrate the feasibility of field randomization of patients with refractory OHCA. This study is using a novel procedure to determine eligibility based on timing and location.

Exploratory: We will collect ECPR process measures including time to confirmed vascular access and confirmed ECPR cannulation. These measures are collected as part of routine clinical care on all patients undergoing ECPR for cardiac arrest at the qualified emergency department(s).

Exploratory: To provide preliminary estimates regarding neurological outcomes following this treatment. This study is not adequately sized to provide meaningful comparative data on neurological outcomes. This aim will provide insight into the proportion of patients with excellent outcomes, along with the proportion of patients with neurologically unsatisfactory outcomes.

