4.2.2 SAFETY ENDPOINTS

Composite safety endpoint of hemorrhage requiring blood transfusion, pneumothorax requiring thoracostomy, hemopericardium requiring pericardiocentesis.

Composite safety endpoint of, hemorrhage requiring blood transfusion (greater than 4 units packed red blood cells per incident), vessel damage requiring vascular procedure or leading to occlusion, venous/arterial thromboembolism, stroke, renal failure and infection

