4.2.3 EXPLORATORY ENDPOINTS

Additional safety outcomes: Splenic injury, liver injury, and all individual components of the composite endpoints listed in 4.2.2

All participants: Utility weighted modified Rankin Scale and cerebral performance category at hospital discharge and 90 days.

Randomization feasibility: Number of attempted uses of randomization app versus successful enrollments

Patient reported outcomes: Neuro-QOL

Cognitive functioning outcomes: NIH-Toolbox

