8 ASSESSMENT OF SAFETY

8.1 SPECIFICATION OF SAFETY PARAMETERS

Predefined safety clinical events are outlined in the endpoints sections 4.2.2 and 4.2.3. Since the study intervention is early transport versus continued resuscitation in the field, and all interventions occurring after this intervention represent standard care, safety endpoints will provide a qualitative assessment of the strategies given the limited sample size. Summaries of

events by group will be provided to all relevant monitoring bodies. Given the severity of cardiac arrest, most patients will experience one or more SAEs as part of routine clinical care.

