8.2 CLASSIFICATION OF AN ADVERSE EVENT

8.2.1 SEVERITY OF EVENT

‘Severity’ is not the same as ‘serious.’ Serious is based on patient/event outcome or action criteria usually associated with events that pose a threat to a patient’s life or health. The term ‘severe’ is often used to describe the intensity (severity) of a specific event (as in mild, moderate, severe myocardial infarction); the event itself, however, may be of relatively minor medical significance (such as severe headache). Seriousness (not severity) serves as a guide for defining regulatory reporting obligations. Most AEs include clinical criteria that describe patient/event outcomes or indicated interventions to more clearly substantiate seriousness.

All adverse events occurring within 24 hours of study enrollment and all serious adverse events occurring during study participation will be documented on the AE case report form. Adverse events will be documented using the NCI Common Terminology Criteria for Adverse Events Version 3.0 (CTCAE). The CTCAE provides descriptive terminology that will be used for recording and reporting adverse events that occur in the EROCA trial. The CTCAE provides a grading (severity) scale for each AE term and AEs are listed alphabetically within categories based on anatomy or pathophysiology. The CTCAE (v 3.0) displays Grades 1-5 with unique clinical descriptions of severity for each AE based on this general guidance:

Grade 1:	Mild AE
Grade 2:	Moderate AE
Grade 3:	Severe AE
Grade 4:	Life-Threatening or Disabling AE
Grade 5:	Death related to AE

Note: Severity is not equivalent to seriousness. A serious adverse event (SAE) would be any event in category 4 or 5, and any event in category 3 that required or prolonged hospitalization.

Not all grades are appropriate for all AEs. Therefore, some AEs are listed with fewer than five options for Grade Selection i.e., Grade 5 (Death) is not appropriate for some AEs and therefore is not an option. A version of the CTCAE is available in the MoP

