8.2.2 RELATIONSHIP TO STUDY AGENT

The site principal investigator is responsible for designating, at the time an AE is reported, how likely it is that the AE is caused by the study intervention. This determination requires clinical judgement, but for purposes of this study an algorithm is used to help the investigator provide reporting that is as objective as possible and consistent with reporting across the trial.

Modified for EROCA, based upon: Adverse Events Reporting Requirements SOP. NIH-NIAID. <http://www.niaid.nih.gov/ncn/sop/adverseevents.htm> , accessed 11-30-04.

Not related: The temporal relationship between treatment exposure and the adverse event is unreasonable or incompatible and/or adverse event is clearly due to extraneous causes (e.g., underlying disease, environment)

Unlikely: May have reasonable or only tenuous temporal relationship to intervention. Must meet both of the following conditions:

- Could readily have been produced by the subject's clinical state, or environmental or other interventions.
- Does not follow known pattern of response to intervention.

Possibly: Must meet any 2 of the 3 following conditions

- Has a reasonable temporal relationship to intervention.
- Could not readily have been produced by the subject's clinical state or environmental or other interventions.
- Follows a known pattern of response to intervention.

Probably: Must meet all 3 of the following conditions

- Has a reasonable temporal relationship to intervention.
- Could not *readily* have been produced by the subject's clinical state or have been due to environmental or other interventions.
- Follows a known pattern of response to intervention.

Definitely: Must meet all 3 of the following conditions

- Has a reasonable temporal relationship to intervention.
- Could not *possibly* have been produced by the subject's clinical state or have been due to environmental or other interventions.
- Follows a known pattern of response to intervention.

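### Section 10.4.4 summarizes only SAEs, so the non-serious AEs and relatedness ratings behind the safety objective enter no planned table, and no overall or by-arm estimate of the 4.2.2 composites is explicitly named

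*Combined protocol and SAP*

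**What the plan says.** Section 3 gives the safety objective: "To estimate frequency of adverse events associated with study interventions". The same section warns that the trial is too small for meaningful comparison between arms.

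Data collection matches that objective. Section 8.2.1 states: "All adverse events occurring within 24 hours of study enrollment and all serious adverse events occurring during study participation will be documented". Sections 8.3 and 8.4.1 repeat the two windows (24 hours for non-serious events, up to 90 days for SAEs). On causality, 8.2.2 says: "The site principal investigator is responsible for designating, at the time an AE is reported, how likely it is that the AE is caused", on a scale with five levels.

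The analysis, for the intent-to-treat population, is in 10.4.4: "We will summarize SAEs by study group (early transport versus usual care) and provide a listing of all SAEs for each of the patients". Nothing else is planned there.

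Two other groups of safety measures are defined. Section 4.2.2 has two composites, the first being "Composite safety endpoint of hemorrhage requiring blood transfusion, pneumothorax requiring thoracostomy, hemopericardium requiring pericardiocentesis". Section 4.2.3 lists as exploratory "Splenic injury, liver injury, and all individual components of the composite endpoints listed in 4.2.2". Section 10.4.11 summarizes exploratory endpoints as event rates with by-arm tables or graphs, and 10.4.8 tabulates the defined safety endpoints by subgroup.

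Among the risks of CPR, 2.3.1 notes: "Rib fractures and solid organ injuries (liver and spleen) are additional potential risks". Section 13.1 lists rib fractures again among the risks of transport with mechanical CPR that are weighed against expected benefit.

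**The concern.** The objective covers adverse events in general and asks about those associated with the interventions. The named safety analysis covers serious events only and does not use the relatedness rating. A non-serious harm can therefore be recorded and rated, yet appear in no planned summary. Rib fracture is the clearest case: the protocol names it as a risk, but it is in neither 4.2.2 nor 4.2.3, so unless it is serious no table shows it.

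The SAE summary is also a weak substitute for intervention harm in this population. Section 8.1 says so in effect: "Given the severity of cardiac arrest, most patients will experience one or more SAEs as part of routine clinical care". If most patients in both arms have an SAE because of the arrest, a count of patients with SAEs mostly describes the arrest.

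This matters more than usual because patients are enrolled without prior consent, on an argument that sets named risks against expected benefit. The report should be able to say how often those risks occurred.

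**Working it through.** **1. Trace each item from collection to table.**

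| Item | Where collected or defined | Planned summary in section 10 |
|---|---|---|
| SAEs | 8.2.1, 8.4.1, 8.4.2 | 10.4.4: by arm, plus a listing |
| Non-serious AEs to 24 hours | 8.2.1, 8.3, 8.4.1 | none named |
| Relatedness, five levels | 8.2.2 | none named |
| Rib fracture, if not serious | risk in 2.3.1 and 13.1; in neither 4.2.2 nor 4.2.3 | none named |
| Components of the composites; liver and spleen injury | 4.2.3 | 10.4.11: event rates by arm |
| Composites at patient level | 4.2.2 | 10.4.8: by subgroup; overall and by arm not explicitly named |

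**2. Component rates do not give the composite.** With k components occurring in x1, ..., xk of n patients, the number of patients with the composite lies between max(x1, ..., xk) and min(n, x1 + ... + xk). Where it falls depends on how many patients have several events. The rates from 10.4.11 therefore leave the composite undetermined unless it is tabulated itself.

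**3. How far deaths could fill an any-SAE count.** Inputs: 408 treated and 30 discharged alive in 2014 (13.1); 30 patients (10.5); allocation 4:1 (10.6.1), so 30 x 4/5 = 24 early transport and 30 x 1/5 = 6 usual care.

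- The plan's own figure first: 30/408 = 7.4%, as stated. Not surviving: (408 - 30)/408 = 378/408 = 92.6%.
- Usual care: 6 x 0.926 = 5.6 expected deaths; the chance that all six die is (378/408)^6 = 0.63.
- Early transport: 2.3.2 quotes 4-33% survival with good neurologic function. Taking that as survival (an assumption), expected deaths are 24 x (1 - 0.33) = 16.1 to 24 x (1 - 0.04) = 23.0.

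If death from the qualifying arrest is recorded as an SAE, deaths alone would put about 93% of usual-care and about 67-96% of early-transport patients in an any-SAE row.

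**4. What the missing tables could show.** Exact (Clopper-Pearson) 95% limits; for 0/n the upper limit is 1 - 0.025^(1/n).

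| Observed | 95% CI |
|---|---|
| 0/6 | 0-45.9% |
| 1/6 | 0.4-64.1% |
| 0/24 | 0-14.2% |
| 3/24 | 2.7-32.4% |
| 6/24 | 9.8-46.7% |
| 3/30 | 2.1-26.5% |

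The early-transport and overall figures are usable as rough estimates; the usual-care figures are barely informative. The primary sample size, alpha and power are unaffected.

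**The case against.** Much of the safety content is planned elsewhere. Most harms named in 2.3.1 are components of the composites or are listed in 4.2.3: pneumothorax, hemopericardium, hemorrhage, vascular injury, thromboembolism, stroke, renal failure, infection, and liver and spleen injury. Through 10.4.11 these get event rates by arm. Section 10.4.3 calls all clinical endpoints exploratory, which arguably brings the composites into 10.4.11 as well. Section 8.1 promises event summaries by group to the monitoring bodies, not limited to SAEs, and 10.4.7.1 has the DSMB review the main safety endpoints.

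This stands, and it rules out one tempting inference: that the plan yields no frequencies of intervention-related harm. What remains is narrower. The protocol keeps safety and exploratory endpoints apart in the synopsis, in section 3 and in 4.2.2 versus 4.2.3, and 4.2.3 brings in only the components. The assignment of the composites is therefore unclear rather than absent. Summaries for monitoring bodies do not define the final analysis.

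A reader might also infer that the SAE table is bound to be swamped by deaths. The documents do not establish that. Section 10.4.4 specifies no any-SAE row; a summary by CTCAE term would separate death from other events, and a listing for 30 patients shows each SAE. Whether death from the qualifying arrest counts as an SAE is unsettled: 8.3 treats conditions present at screening as baseline but records deterioration. The 92.6% refers to all treated arrests, not refractory ones.

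Nor can the omission of rib fractures be sized. The documents give no frequency, and a rib fracture meeting the SAE definition would be in the SAE summary.

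Finally, by-arm AE rates are hard to interpret. Mechanical CPR is part of standard care (7.1.2), and for patients pronounced dead in the field the source is the EMS run report (7.1.1). Injuries are more likely to be found in those who reach hospital. This is a reason for a caveat, not for omitting the table.

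**Conclusion.** The stated safety analysis is narrower than the stated safety objective. Non-serious AEs within 24 hours and the relatedness ratings are collected and enter no planned table, and no passage explicitly names an overall or by-arm patient-level estimate of the 4.2.2 composites. These conclusions come from the text and need no assumption.

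That an SAE count not split by relatedness says little about intervention harm rests on the expectation in 8.1. The figures of about 5.6 of 6 and 16 to 23 of 24 illustrate this. They assume that death from the arrest is recorded as an SAE, that the 2014 registry rate applies to usual care, and that 4-33% can stand for survival with early transport.

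The gap is modest in a 30-patient feasibility trial with no planned safety comparison, but it is worth closing because the data are already on the AE form.

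**What to change.** Reword 10.4.4 to report descriptively, by arm and overall, the number and proportion of patients with exact 95% CIs for:

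- (a) each composite safety endpoint, after the definitions are reconciled. The synopsis has one composite and 4.2.2 has two, with different components. The first in 4.2.2 also gives no transfusion volume, while the second and the synopsis do;
- (b) any AE within 24 hours, serious or not, by CTCAE term, so that rib fractures appear under their own term;
- (c) any AE or SAE rated possibly, probably or definitely related under 8.2.2.

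Show death from the index arrest separately from other SAEs, and state whether it is recorded as an SAE. Keep the SAE summary and listing. Add a note that AE detection differs between patients who reach hospital and those pronounced dead in the field, so the by-arm rates are not comparative.

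The cost is SAP wording and a few more tables, with no new patients or data collection. The intervals will be wide, above all in usual care (0/6 gives 0-46%), and should be presented as such.

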10.4.5 ADHERENCE AND RETENTION ANALYSES

We will qualitatively summarize the reasons that patients were randomized but that the assigned early transport or usual care pathways were not followed. We will qualitatively summarize reasons for participant withdrawal.

10.4.6 BASELINE DESCRIPTIVE STATISTICS

We will provide descriptive statistics including demographic variables by study group (early transport versus usual care). As the patients are randomized in the field, no baseline laboratory variables are available. No hypothesis testing will be used to compare the groups due to the small sample size.

10.4.7 PLANNED INTERIM ANALYSES

10.4.7.1 SAFETY REVIEW

The DSMB will review safety data as per their charter. The main listed safety endpoints will be reviewed. No formal statistical boundaries will be used to determine stopping for safety concerns.

10.4.7.2 EFFICACY REVIEW

We will not employ formal stopping rules for efficacy or futility given the small sample size of the study

10.4.8 ADDITIONAL SUB-GROUP ANALYSES

We will pre-specify subgroup analyses of the primary endpoints by gender, age (less than 50 versus 51-70), diabetes, prior cardiac disease, and race/ethnicity. These subgroup analyses will be presented graphically and in tables. Given the small sample size formal hypothesis testing will not be performed. In addition, we will also categorize the defined safety endpoints by each of the subgroups mentioned above, graphically and in tables.

10.4.9 MULTIPLE COMPARISON/MULTIPLICITY

We are employing two primary endpoints, but no adjustment for multiplicity will be performed as the process endpoint is a threshold.

10.4.10 TABULATION OF INDIVIDUAL RESPONSE DATA

Individual participant data for the primary endpoints will be summarized in tabular form. We will also include exploratory endpoint data (mRS and CPC) in these tables.

10.4.11 EXPLORATORY ANALYSES

Each of the exploratory endpoints will be summarized using appropriate techniques based on the distribution (for continuous variables) or event rates (for categorical variables). Group (early transport versus usual care) comparisons will be presented in graphical, or tabular form for the exploratory endpoints. Formal hypothesis testing will be avoided given the small sample size.

10.5 SAMPLE SIZE

Based on 2014 data, we expect approximately 20 unique visits in one year to qualify, thus in 18 months we expect 30 patients to qualify with the protocol used on at least 24 (80%) of these. With 24 patients, if we find that 19/24 (79.2%) of cases meet time limit we have 98% power to find that the proportion of patients arriving at the ED within 30 minutes is significantly different than in 2014. The protocol will be deemed optimal if $\geq 19/24$ patients are transported to the ED within 30 minutes (95% CI lower bound 62.6%).

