10 STATISTICAL CONSIDERATIONS

10.1 STATISTICAL AND ANALYTICAL PLANS

This is a pilot trial, designed to demonstrate proof of feasibility prior to a larger scale trial that will be powered to improve patient outcomes. The primary endpoints target process measures, namely the delivery of randomized patients to the qualified ED within 30 minutes of qualifying event.

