10.2 STATISTICAL HYPOTHESES

- Co-Primary Endpoint(s): Arrival to qualified ED within 30 minutes

We hypothesize that the proportion of patients randomized to early transport arriving at the hospital within 30 minutes will be greater than the historical proportion of 38.7%.

- Co-Primary Endpoint(s): Initiation of ECPR within 30 minutes of ED arrival

We hypothesize that greater than or equal to 80% of patients will have ECPR (qualifying ED standard care process) initiated within 30 minutes of ED arrival.

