10.4.2 ANALYSIS OF THE PRIMARY EFFICACY ENDPOINT(S)

Co-Primary Endpoint(s): Arrival to qualified ED within 30 minutes

The proportion of qualifying episodes to arrive at the ED within 30 minutes will be compared to our historical data point estimate of 38.7% using a one sample exact test of binomial proportions at the 0.05 two-sided significance level.

Co-Primary Endpoint(s): Initiation of ECPR within 30 minutes of ED arrival

Using the modified intention to treat population with ongoing cardiac arrest in the qualified ED, we will declare the analysis of this objective successful if 80% or more of patients have ECPR (qualifying ED standard care process) initiated within 30 minutes of ED arrival. No formal hypothesis test will be conducted.

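### Section 10.5 prints a 95% lower bound of 62.6% beside the bar of 19/24, but the exact bound for 19/24 is 57.8%; 62.6% is the exact bound for 20/24

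*Combined protocol and SAP*

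**What the plan says.** Section 10.5 (Sample Size) expects 30 qualifying patients in 18 months and takes 24 of them as the working number: "thus in 18 months we expect 30 patients to qualify with the protocol used on at least 24 (80%) of these". It then states the power: "With 24 patients, if we find that 19/24 (79.2%) of cases meet time limit we have 98% power" to detect a difference from 2014. The next sentence sets a second criterion. The protocol is deemed optimal if at least 19/24 "patients are transported to the ED within 30 minutes (95% CI lower bound 62.6"%). No interval method is given there or elsewhere for this bound.

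Section 10.4.2 compares the on-time proportion with the historical 38.7% "using a one sample exact test of binomial proportions at the 0.05 two-sided significance level". Section 10.2 gives the direction of the hypothesis: the proportion "will be greater than the historical proportion of 38.7"%.

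**The concern.** The printed lower bound does not go with the printed count under the method that the plan uses for this endpoint. The bound tells a reader what true on-time rate a result at the bar would rule out. Section 10.1 says of the study: "This is a pilot trial, designed to demonstrate proof of feasibility prior to a larger scale trial". That makes the bound part of the feasibility message, although no decision is computed from it.

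There are two possible faults, with different consequences:

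- **The bound is wrong.** Section 10.5 then overstates the precision at the bar. A later report of 19/24 with an exact interval would visibly disagree with the plan.
- **The count is wrong and the bar was meant to be 20/24.** A result of exactly 19 on time would then be labelled differently.

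**Working it through.** **Inputs.** n = 24, the count 19 (79.2%), the power of 98% and the bound of 62.6% come from section 10.5. The null value 38.7% and the exact two-sided test at 0.05 come from section 10.4.2.

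**Step 1: reproduce the plan's power.** With X ~ Binomial(24, 0.387) under the null, the two-sided exact p-value is 0.059 at 14 and 0.021 at 15, so the test rejects upward from 15/24. Power at a true rate of 19/24 is P(X ≥ 15) = 0.983. This matches the printed 98%. At a true rate of 20/24 it would be 0.997. The power statement therefore fits exact methods and the count 19.

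**Step 2: exact lower bound.** The Clopper-Pearson limits for x of n are the Beta quantiles L = B(0.025; x, n − x + 1) and U = B(0.975; x + 1, n − x).

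- 19/24: L = B(0.025; 19, 6) = 0.5785 and U = B(0.975; 20, 5) = 0.9287, so 57.8% to 92.9%.
- 20/24: L = B(0.025; 20, 5) = 0.6262 and U = B(0.975; 21, 4) = 0.9526, so 62.6% to 95.3%.

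Direct check: L should be the rate at which the upper tail equals 0.025. At a rate of 0.5785, P(X ≥ 19) = 0.0250. At a rate of 0.626, P(X ≥ 19) = 0.067, so 19/24 does not exclude 62.6% by the exact method, whereas P(X ≥ 20) = 0.0249.

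A scan of every count with n from 15 to 40 finds only one whose exact 95% lower bound rounds to 62.6%, and that is 20/24.

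**Step 3: can another method give 62.6% from 19/24?** Here p = 0.7917 and SE = √(0.7917 × 0.2083 / 24) = 0.0829.

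| Method, two-sided 95%, 19/24 | Lower bound | Printed 62.6% minus this |
|---|---|---|
| Exact | 57.8% | 4.8 |
| Agresti-Coull | 59.1% | 3.5 |
| Wilson | 59.5% | 3.1 |
| Jeffreys | 60.2% | 2.4 |
| Wald with continuity correction | 60.8% | 1.8 |
| Wald, p − 1.96 SE | 62.9% | −0.3 |
| p − 2 SE | 62.59% | 0.0 |
| Wald with n − 1 in the variance | 62.57% | 0.0 |

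A one-sided 95% exact bound for 19/24 is 61.1%, so a one-sided reading does not explain the figure either.

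**Step 4: what one patient would change.** At a true rate of 79.2%, P(X ≥ 19) = 0.617, P(X ≥ 20) = 0.420 and P(X = 19) = 0.617 − 0.420 = 0.197.

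**The case against.** The plan names no interval method in section 10.5, and section 10.4.2 prescribes an exact test, not an exact interval. Two normal-type formulas do give 62.6% from 19/24, and the ordinary Wald bound is only 0.3 points away. On that reading, count and bound already agree, and what remains is a preference for exact over approximate intervals. The case for 20/24 also runs against the text: 19/24 is printed twice, once with its correct percentage, and the power fits 19/24. The scan that singles out 20/24 looks only at exact bounds. Finally, nothing in the plan depends on 62.6%.

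Much of this stands. The origin of the figure cannot be settled from the documents, 20/24 is not shown to be the intended bar, and the practical effect is small. It does not clear the printed line, though. The two formulas that reach 62.6% are non-standard, neither fits the exact test, and both give a more favourable bound than the exact one. If one of them was used, section 10.5 carries an unlabelled approximation that disagrees with the planned analysis. The remedy is the same whichever explanation is true.

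**Conclusion.** The concern holds, as a minor one. Taking the exact interval as the counterpart of the exact test in section 10.4.2, the lower bound at the bar of 19/24 is 57.8%, and the printed 62.6% overstates it by 4.8 points. That 62.6% is the exact bound for 20/24 is certain. That a wrong count explains the figure is only a possibility, and the text favours 19/24.

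The primary test, the 98% power and the sample size are unaffected. A result of 19/24 is clearly significant against 38.7% (exact two-sided p about 0.00007), and 57.8% exceeds 38.7% by 19.1 points. What changes is either the precision claimed at the bar or, if 20/24 was intended, the bar itself by one patient. In the second case a result of exactly 19/24, with a 19.7% chance at a true rate of 79.2%, would change label.

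**What to change.** Ask the sponsor which count was intended, name the interval method in section 10.5, and make count and bound agree:

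- **If 19/24 stands**, as the present text suggests, replace the bound of 62.6% with an exact (Clopper-Pearson) 95% lower bound of 57.8%.
- **If the sponsor confirms 20/24**, correct the bar and keep 62.6%, labelled exact.

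The cost is one query and one corrected line. In the first case the stated bound becomes less favourable. In the second the bar is harder to reach: 42.0% rather than 61.7% at a true rate of 79.2%.

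An optional clarification, not a correction: say that the 98% power belongs to the test against 38.7%, which rejects from 15/24, and that the chance of reaching 19/24 at a true rate of 79.2% is about 62%.
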